7.1.1 Induction therapy phase

Eligible patients will be randomized before proceeding to 7+3, or within one week of starting 7+3 in 1:1 ratio, to 7+3 alone or 7+3+ Pembrolizumab (MK-3475). As shipment of pembrolizumab to site can only be ordered after randomization, every effort should be done to randomize the patient as soon as possible. See Section 9.1 for agent ordering information. If patient is randomized after initiation of 7+3 therapy, the patient should continue to meet all eligibility criteria up to randomization date. Planned stratification factors include 1) age (younger than 65 vs. 65 and older), 2) cytogenetics **by FISH or metaphase karyotype** (presence vs. absence of core binding factor inversions and translocations), and 3) **t- AML or AML arising from prior/antecedent MDS (yes/no)**. All patients will receive cytarabine at 100 mg/m²/day continuous infusion on Days 1-7 and either idarubicin 12 mg/m²/day IV on Days 1-3 or daunorubicin 60 mg/m²/day IV on Days 1-3. A bone marrow biopsy on Day 14 (between Days 14 and 21) will be performed to assess for chemoablation. If patients have evidence of residual leukemia (defined as per institutional practice) in their bone marrow and following assessment by repeat transthoracic echocardiography (TTE) for assessment of ejection fraction, they will receive re-induction 5+2 chemotherapy, which means patients will receive cytarabine at 100 mg/m²/day continuous infusion on Days 1-5 and either idarubicin 12 mg/m²/day IV or daunorubicin 60 mg/m²/day IV on Days 1-2. Anthracycline dosing adjustments may need to be made, per institutional guidelines. Regardless of chemoablation status, on Day 8 of the induction chemotherapy and Q3W (±3 days) thereafter, half of the patients will receive Pembrolizumab (MK-3475) IV (intervention arm). The other half will not receive Pembrolizumab (MK-3475) (control arm). At time of count recovery, defined as platelet count more than 50,000 or neutrophil count more than 500, patients will undergo a bone marrow aspirate/biopsy in order to assess for response and MRD. If there is no count recovery, a bone marrow will have to be performed by day 42. If the bone marrow shows hypoplasia and patient remains without count recovery, a bone marrow will be performed q 2 weeks (+/- 3 days) till there is count recovery or evidence of persistent AML. If patients have a CR or a CRi, patients will continue with consolidation therapy. If patients do not achieve a CR or CRi, they will be taken off study. If Pembrolizumab is discontinued for any reason (after at least one dose of Pembrolizumab, the patient should continue on 7+3 or Re-Induction on study.

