7.1.2 Consolidation therapy phase

Consolidation therapy will consist of up to four cycles of infusional HiDAC and Pembrolizumab (MK-3475) (intervention arm) vs. HiDAC alone (control arm). Patients <60 years of age will receive 3 g/m² every 10-12 hours (Q12H) on Days 1, 3, and 5 (total 6 doses). Patients ≥60 years of age will receive 1.5 g/m² Q12H on Days 1, 3, and 5 (total 6 doses). Cycle 1 of consolidation therapy must start within 4 weeks of documenting remission status. Each cycle lasts ~28 days (up to 42 days). Patients in the intervention arm will continue to receive MK-3475 (pembrolizumab) Q3W (±3 days). Do not administer pembrolizumab concurrently with HiDAC chemotherapy Days 1-5 of each consolidation cycle. For consideration of timing of pembrolizumab, allow at least 3 hours after completion of chemotherapy prior to pembrolizumab

administration. Administration window for pembrolizumab may be extended to allow for this timing as necessary. After Cycle 1 of HiDAC, bone marrow assessment will be performed at the time of count recovery (same rules apply as post induction bone marrow in case of lack of count recovery) for formal assessment of response and MRD. Patients, who remain in CR or CRi, will be allowed to proceed to up to 3 more cycles of HiDAC and Pembrolizumab (MK-3475) (intervention arm) vs. HiDAC alone (control arm). Patients, who are not in CR or CRi will be taken off study. . If Pembrolizumab (MK-3475) is discontinued for any reason (after at least one dose of Pembrolizumab), the patient should continue Consolidation therapy on study.

Consolidation Therapy Regimen Description					
Agent	Premedications ; Precautions	Dose*	Route	Schedule	Cycle Length
Pembrolizumab (MK-3475) (For Intervention Arm only)	Premedication with antipyretic and antihistamine may be considered. No premedication with steroids	200 mg See Section 8.1 for instructions on the preparation of the infusion solution.	IV over 30 minutes (between 25-40 minutes) using an infusion set containing a low-protein binding 0.2 to 5 µm in-line filter. See Section 8.1 for compatible infusion set materials including in-line filter.	Q3W (±3 days) continuous from Day 8 of Induction. For consideration of timing of pembrolizumab, allow at least 3 hours after completion of chemotherapy prior to pembrolizumab administration	28 days (±7 days)

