7.1.3 Maintenance therapy phase

Following count recovery from the last cycle of consolidation therapy, a bone marrow biopsy will be performed to assess for response and MRD. Patients, who remain in CR/CRi will continue on maintenance therapy while patients who do not remain in CR/CRi will be taken off study. Patients in CR/CRi will proceed with single-agent Pembrolizumab (MK-3475) (intervention arm) vs. no maintenance therapy (control arm) Q3W dosing schedule for up to 2 years, calculated from first day of maintenance therapy, according to their original randomization (*i.e.*, there will be no second randomization). For patients randomized to Arm B, Pembrolizumab (MK-3475) will be administered on Day 1 (+/- 3 days) of each maintenance cycle (each maintenance cycle is 21 days). Bone marrow samples will be obtained every 3 months while

patients are receiving maintenance or in observation to assess for MRD. Patients, who are deemed to require HSCT, can forgo any remaining protocol-defined consolidation or maintenance therapy and proceed with HSCT. Patients proceeding with HSCT will be followed for survival and SAEs through the first 100 days post-HSCT including assessment for occurrence of acute and chronic GVHD.

Maintenance Therapy Regimen Description					
Agent	Premedications ; Precautions	Dose	Route	Schedule	Cycle Length
pembrolizumab (MK-3475) (For Intervention Arm only)	Premedication with antipyretic and antihistamine may be considered. No premedication	200 mg See Section 8.1 for instructions on the preparation of the infusion	IV over 30 minutes (between 25-40 minutes) using an	Day 1(+/- 3 days) of each 21-day maintenance cycle	21 Days

Maintenance Therapy Regimen Description					
Agent	Premedications ; Precautions	Dose	Route	Schedule	Cycle Length
	with steroids	solution.	infusion set containing a low-protein binding 0.2 to 5 µm in-line filter. See Section 8.1 for compatible infusion set materials including in-line filter.		

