Bone marrow biopsy	X										X ⁿ				X				X ^o		X	X		X ^s				
Stool	X														X ^z													
Research Blood Draws	X									X ^m	X ⁿ				X				X ^o	X ^q	X ^r	X ^r		X ^s				
Skin Punch Biopsy ^α	X																											
Transthoracic ECHO (TTE) or MUGA	X								X ^t																			
CT chest	X ^s																											

- a If the patient does not have a CR/CRi before starting this part of the study, the patient should go off study. Patients <65 may complete 3-4 cycles of consolidation therapy. Patients ≥65 years old may complete 1-2 cycles of consolidation therapy.
- b End of treatment visit will be immediately following final dose of Pembrolizumab (MK-3475).
- c After completing study treatment, clinical follow-up assessments are required every 6 months from date of therapy discontinuation. Common clinical practice should be monitored by institutional practice (*i.e.*, every 3 months though not required by protocol), but assessment results are only required every 6 months (+/- 14 days). All participants should be followed for survival to 3 years after end of treatment. For patients who achieve undetectable MRD during study treatment, central MRD assessments should continue in addition to general clinical follow.
- d Cytarabine should be dosed as appropriate for each phase of the study. Daunorubicin (60 mg/m²/day) or Idarubicin (12 mg/m²/day)
- e If patient has residual leukemia at the time of bone marrow aspiration, the patient may receive a 5+2 administration of these drugs. Adjust anthracycline dose as per institutional standards for Re- Induction.
- f Only for patients randomized to Arm B at 200 mg. Pembrolizumab (MK-3475) will be administered on Day 8 of induction and then Q3 weeks (+/- 3 days). Do not administer pembrolizumab concurrently with HIDAC chemotherapy Days 1-5 of each consolidation cycle. For consideration of timing of pembrolizumab, allow at least 3 hours after completion of chemotherapy prior to pembrolizumab administration. Administration window for pembrolizumab may be extended to allow for this timing as necessary. Each cycle of Maintenance is 21 days with pembrolizumab given on day 1 of each cycle up to 2 years.
- g Note: Performance status evaluations are based on a 4-week cycle. At minimum, performance status should be evaluated at the beginning of every cycle.

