13.2 Hematologic Response

13.2.1 Complete Response (CR) without minimal residual disease (CRM RD-): If studied pretreatment, CR with negativity for a genetic marker by RT-qPCR, or CR with negativity by MFC

13.2.2 Complete remission (CR): Bone marrow blasts <5%; absence of circulating blasts and blasts with Auer rods; absence of extramedullary disease; ANC $\geq 1.0 \times 10^9/L$ (1000/ μ L); platelet count $\geq 100 \times 10^9/L$ (100 000/ μ L); MRD+ or unknown

13.2.3 CR with incomplete count recovery (CRi): All CR criteria except for residual neutropenia ($< 1.0 \times 10^9/L$ [1000/ μ L]) or thrombocytopenia ($< 100 \times 10^9/L$ [100,000/ μ L])

13.2.4 CR with partial recovery count (CRh): All CR criteria with neutrophil count $\geq 0.5 \times 10^9/L$ and platelet count $\geq 50 \times 10^9/L$. *CRh is being recorded as a separate response criteria from other responses (for example patient could have CRi by traditional criteria but also CRh).*

13.2.5 Hematologic improvement: Erythroid response (E) (pretreatment Hgb < 11 g/dL) Hgb increase by ≥ 1.5 g/dL, Platelet response (P) (pretreatment platelets $< 100 \times 10^9/L$) Absolute increase of $\geq 30 \times 10^9/L$ for patients starting with $> 20 \times 10^9/L$ platelets Increase from $< 20 \times 10^9/L$ to $> 20 \times 10^9/L$ and by at least 100%.

13.2.6 **Morphologic leukemia-free state (MLFS):** Bone marrow blasts <5%; absence of blasts with Auer rods; absence of extramedullary disease; no hematologic recovery required. (Marrow should not merely be “aplastic”; at least 200 cells should be enumerated or cellularity should be at least 10%)

13.2.7 **Partial remission (PR)** All hematologic criteria of CR; decrease of bone marrow blast percentage to 5% to 25%; and decrease of pretreatment bone marrow blast percentage by at least 50%

Peripheral Blood Counts:

- Neutrophil count $\geq 1.0 \times 10^9/L$.
- Platelet count $\geq 100 \times 10^9/L$.
- Reduced hemoglobin concentration or hematocrit has no bearing on remission status.
- Leukemic blasts must not be present in the peripheral blood.

Bone Marrow Aspirate and Biopsy:

- Cellularity of bone marrow biopsy must be >20% with maturation of all cell lines.
- <5% blasts
- Auer rods must not be detectable.

Extramedullary leukemia, such as CNS or soft tissue involvement, must not be present.

13.2.8 **Stable disease:** Absence of CRMRD–, CR, CRi, PR, MLFS; and criteria for PD not met.

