Note: stable disease would not count as an adequate response in terms of response assessment for study purposes. However, some patients with stable disease can also achieve hematologic improvements such as transfusion independence without reduction in blasts, and some patients on immunotherapy arm might need longer time than 6 months to respond or could have more stable disease that translates into longer survival in this randomized study. Furthermore, there are very few options available for most patients after azacitidine-venetoclax and therefore it is imperative to ensure patients can have the opportunity to achieve maximal benefit from this therapy. We therefore will allow the treating investigator to keep patients on treatment with stable disease at their discretion if they judge the patient to be deriving clinical benefit on study.

13.2.9 **Progressive disease (PD):** Evidence for an increase in bone marrow blast percentage and/or increase of absolute blast counts in the blood.

- >50% increase in marrow blasts over baseline (a minimum 15% point increase is required in cases with <30% blasts at baseline; or persistent marrow blast percentage of >70% over at least 3 mo; without at least a 100% improvement in ANC to an absolute level ($>0.5 \times 10^9/L$ [$500/\mu L$], and/or platelet count to $>50 \times 10^9/L$ [$50\,000/\mu L$] non-transfused)
- >50% increase in peripheral blasts ($WBC \times \% \text{ blasts}$) to $>25 \times 10^9/L$ ($>25\,000/\mu L$) (in the absence of differentiation syndrome)
- New extramedullary disease Some protocols may allow transient addition of hydroxyurea to lower blast counts.

“Progressive disease” is usually accompanied by a decline in ANC and platelets and increased transfusion requirement and decline in performance status or increase in symptoms.

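### The stable-disease note in Section 13.2.8 lets investigators keep patients without CR/CRi on treatment, against the off-study rules in 7.1.1 to 7.1.3 and Study Calendar footnote a

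*Combined protocol and SAP*

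**What the plan says.** Section 13.2.8 defines stable disease as the absence of MRD-negative CR and then of "CR, CRi, PR, MLFS; and criteria for PD not met". The note that follows opens by saying that stable disease is not an adequate response for study purposes. It then gives reasons for continuing anyway: "some patients on immunotherapy arm might need longer time than 6 months to respond", and "there are very few options available for most patients after azacitidine-venetoclax". It concludes: "We therefore will allow the treating investigator to keep patients on treatment with stable disease at their discretion". The permission depends on the investigator judging that the patient benefits clinically.

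The treatment plan says otherwise, in four places:

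- Section 7.1.1, after induction: "If patients do not achieve a CR or CRi, they will be taken off study".
- Section 12, Study Calendar footnote a, marked on the consolidation heading and on Cycle 2: "If the patient does not have a CR/CRi before starting this part of the study, the patient should go off study".
- Section 7.1.2, after consolidation cycle 1: "Patients, who are not in CR or CRi will be taken off study".
- Section 7.1.3, before maintenance: "patients who do not remain in CR/CRi will be taken off study".

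The only allowance is in Section 7.1.1, and 7.1.2 carries it over. A hypoplastic marrow without count recovery is repeated every 2 weeks until counts recover or persistent AML is shown.

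**The concern.** A site with a patient who has persistent AML after induction can find support for either action. The stopping list in Section 7.3 does not settle the matter: it names progression but not failure to reach CR/CRi. The stated reason does not fit the trial either, because patients are randomized to 7+3 with or without pembrolizumab. Section 10.4.2.1.2 also mentions Aza + Ven arms that this trial lacks. That suggests the text was carried over from another protocol, but this origin is an inference.

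What is at stake is patient management and exposure. While a patient stays on protocol therapy, other anti-leukemia treatment is barred (7.1, 7.2.1) unless the patient is removed from the trial or the study chair and CTEP agree case by case. Retention could therefore delay salvage treatment and add pembrolizumab exposure that the treatment plan does not intend.

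**Working it through.** **1. The rules side by side**

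| Decision point | Treatment plan or calendar | 13.2.8 note |
|---|---|---|
| End of induction (marrow day 28 to 42) | No CR/CRi: off study (7.1.1, footnote a) | Stable disease may continue if judged beneficial |
| After consolidation cycle 1 | No CR/CRi: off study (7.1.2, footnote a) | Same |
| After last consolidation, before maintenance | No CR/CRi: off study (7.1.3) | Same |

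That is four statements at three decision points. None refers to 13.2.8 or makes an exception for stable disease. Because stable disease excludes CR and CRi, every patient the note covers is one the plan takes off study.

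**2. Where the conflict arises.** After a remission, marrow blasts of 5% or more count as relapse under Appendix D. The clash therefore falls mainly at the end of induction. The repeat-marrow allowance does not remove it, since that allowance ends once persistent AML is shown.

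**3. Can the category be assigned at that point?** Appendix D says stable disease should last at least 3 months. Taking 6 months as 183 days, 3 months is about 91 days (183 / 2 = 91.5). The end-of-induction marrow is due by day 42, and 42 < 91. A patient handled under 7.1.1 has left before the duration can be met. Section 13.2.8 itself does not repeat the 3-month requirement.

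**4. What continuation would consist of.** Consolidation cycle 1 must start within 4 weeks of documented remission (7.1.2), and the control arm has no maintenance drug (7.1.3). Pembrolizumab is scheduled every 3 weeks from day 8. So for a patient not in remission after induction, it is the only agent with a schedule that runs on.

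**5. Illustration of exposure.** Scheduled dose days are 8 + 21k, for k = 0, 1, 2, and so on.

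- By day 42: days 8 and 29, so 2 doses.
- By day 183: days 8, 29, 50, 71, 92, 113, 134, 155 and 176, so 9 doses.
- Difference: 9 − 2 = 7 further doses.

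The window of 3 days either way does not alter these counts (29 + 3 = 32 and 50 − 3 = 47; 176 + 3 = 179 and 197 − 3 = 194). The matching control patient has 0 further scheduled doses of any study drug.

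**6. Design figures.** With 25 per arm, rates of 50% and 75%, and one-sided alpha 0.1 (z = 1.2816), the pooled rate is 0.625. The null standard error is √(2 × 0.625 × 0.375 / 25) = 0.1369. The alternative standard error is √((0.25 + 0.1875) / 25) = 0.1323. Power = Φ((0.25 − 1.2816 × 0.1369) / 0.1323) = Φ(0.563) = 0.713, which agrees with the stated value of about 71%. Nothing in this calculation depends on the note.

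**The case against.** The best defence is that the note is close to inoperative leftover text. The off-study rule acts before 3 months of stability can be shown, and later loss of remission is usually relapse. The permission is also narrower than the quoted sentence alone suggests, because it requires judged clinical benefit. It does not trap anyone: the investigator chooses continuation and can stop treatment under Section 7.3. All of this stands, and it is why the severity is minor. It does not remove the contradiction. Section 13.2.8 omits the 3-month condition, and no text says which instruction governs.

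A reader might infer three stronger things that the documents do not support.

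- **That the better responses, PR and MLFS, must always leave while stable disease stays.** MLFS needs no count recovery and can have cellularity as low as 10%. A patient with a hypoplastic marrow and no count recovery is re-tested under 7.1.1, not removed.
- **That use would be unequal by arm.** The late-response reason names the immunotherapy arm, but the permission covers patients in both arms. Continuation mainly in the pembrolizumab arm is a probable consequence of the schedules, not something the plan states.
- **That about 7 of 25 patients would be affected.** The front-line nivolumab study cited in Section 2 had 32 − 23 = 9 of 32 patients without CR/CRi. That study used a different drug and cytarabine dose, and its count may include PR, MLFS, progression and death. It does not estimate stable disease here.

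**Conclusion.** The contradiction is real, stands in current operative text, and rests on a rationale that fits neither arm. Sites have opposite instructions on whether a patient with persistent AML stays on protocol therapy. The text is wrong as written, at minor severity.

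The size is limited. The number of patients affected is unknown. The 7 further doses are an illustration only: they assume a day-8 start, continuation from a day-42 marrow, and a stop at day 183. The plan sets no such horizon.

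A reader might also infer bias in the primary comparison or an inflated type I error. The documents do not support that. Section 10.5.2 counts patients without CR/CRi after induction and first consolidation as treatment failures, and Section 13.1 counts drop-outs as not MRD-negative. The note itself says that stable disease is not an adequate response. Any effect would be on exposure, safety and possibly later outcomes through delayed salvage, and none of these can be quantified from the documents.

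**What to change.** In the Section 13.2.8 note, keep the opening sentence that stable disease is not an adequate response for study purposes. Delete everything after it: the late-response, azacitidine-venetoclax and continuation text. Sections 7.1.1 to 7.1.3 and footnote a then govern both arms, and patients who go off study are still followed for survival and remission status under Section 7.4. Section 10.5.2 needs no change.

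If the sponsor does want continuation in stable disease, the exception has to be written into 7.1.1 to 7.1.3 and footnote a, with a rationale that applies to this trial.

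The cost is a wording amendment. The sample size of 50, the one-sided alpha of 0.1 and the power of about 71% stay as they are.

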13.2.9.1 MRD Response

Refer to section

9.1.1

13.3 Other Response Parameters

- EFS or RFS will be calculated as the time from initial treatment to either disease relapse or death. Duration of response or remission duration will be calculated as the time from first CR to the date of the first documented relapse or death, whichever occurs first. OS will be calculated from time from initial treatment to death.

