1.2 Secondary Objectives

- 1.2.1 Assess the rate of complete remission (CR) / complete remission with incomplete count recovery (CRi) as defined per European Leukemia Net 2017 response criteria at time of count recovery after induction therapy with chemotherapy + Pembrolizumab (MK-3475) (Dohner *et al.*, 2017).
- 1.2.2 Rates of complete remission with partial recovery count (CRh) and Hematologic improvement (HI) to red blood cells and platelets
- 1.2.3 Assess the rates of MRD negativity at Day 14, MRD-negative CR at end of induction therapy and MRD negative CR after last consolidation cycle.
- 1.2.4 Assess event free survival (EFS), measured from randomization to failure to achieve CR/CRi, relapse or death from any cause, and relapse free survival (RFS), calculated as the time from first documentation of CR/CRi to either disease relapse or death from any cause.
- 1.2.5 Assess the duration of response (DOR, defined as the time from first CR/CRi to the date of the first documented relapse or death, whichever occurs first) and overall survival (OS), defined as time from randomization to death from any cause.
- 1.2.6 Assess safety endpoints including proportion of patients who develop severe toxicity as defined in the protocol.

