10.4 Analysis of Secondary and Exploratory Endpoints

10.4.1 Secondary Endpoints

10.4.1.1 Efficacy Endpoints:

- Assess the rate of CR/CRi as defined per the ELN 2017 (see Appendix D) response criteria at time of count recovery after induction therapy with chemotherapy + Pembrolizumab (MK-3475).
- Assess MRD negativity at Day 14.
- Assess the rate of MRD-negative CR at end of induction therapy.
- Assess the rate of MRD-negative CR at end of consolidation.
- Assess rates of complete remission with partial recovery count (CRh) and Hematologic improvement (HI) to red blood cells and platelets.
- Assess the percentage of patients with MRD-CR at time of count recovery after first cycle of consolidation therapy using a MRD cut-off of 0.01%.
- Assess EFS, RFS, calculated as the time from initial treatment to either disease relapse or death.
- Assess the DOR (defined as the time from first CR to the date of the first documented relapse or death, whichever occurs first) and OS.

10.4.1.2 Safety Endpoints:

- Assess safety endpoints including proportion of patients who develop severe toxicity.

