- >50% increase in marrow blasts over baseline (a minimum 15% point increase is required in cases with <30% blasts at baseline; or persistent marrow blast percentage of >70% over at least 3 mo; without at least a 100% improvement in ANC to an absolute level ($>0.5 \times 10^9/L$ [$500/\mu L$], and/or platelet count to $>50 \times 10^9/L$ [$50\,000/\mu L$] nontransfused)
- >50% increase in peripheral blasts (WBC \times % blasts) to $>25 \times 10^9/L$ ($>25\,000/\mu L$) (in the absence of differentiation syndrome)
- New extramedullary disease Some protocols may allow transient addition of hydroxyurea to lower blast counts

“Progressive disease” is usually accompanied by a decline in ANC and platelets and increased transfusion requirement and decline in performance status or increase in symptoms

Relapse

Hematologic relapse (after CRMRD⁻, CR, CRi) Bone marrow blasts $\geq 5\%$; or reappearance of blasts in the blood; or development of extramedullary disease

Molecular relapse (after CRMRD⁻) If studied pretreatment, reoccurrence of MRD as assessed by RT-qPCR or by MFC

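### Section 13.3 gives EFS and RFS a single formula that contradicts objective 1.2.4, and three-year data collection in 10.1 cannot support the five-year analysis planned beside it

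*Combined protocol and SAP*

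**What the plan says.** **Endpoint definitions.** The secondary objectives (1.2.4 and 1.2.5) define each endpoint separately:

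- EFS: "Assess event free survival (EFS), measured from randomization to failure to achieve CR/CRi, relapse or death from any cause".
- RFS: "relapse free survival (RFS), calculated as the time from first documentation of CR/CRi to either disease relapse or death from any cause".
- DOR: "DOR, defined as the time from first CR/CRi to the date of the first documented relapse or death, whichever occurs first".
- OS starts at randomization.

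Section 13.3 gives a second set:

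- EFS and RFS together: "EFS or RFS will be calculated as the time from initial treatment to either disease relapse or death".
- DOR: "Duration of response or remission duration will be calculated as the time from first CR to the date of the first documented relapse or death".
- OS: "OS will be calculated from time from initial treatment to death".

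The list of secondary efficacy endpoints in 10.4.1.1 has: "Assess EFS, RFS, calculated as the time from initial treatment to either disease relapse or death". It also starts DOR at first CR. I found no statement of which section prevails.

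**Length of follow-up.** There are three statements. Section 7.4 follows survival and remission status for up to 5 years from randomization. The follow-up paragraph of 10.1 collects survival and disease status for up to three years from first dose, and its next sentence but one step on plans a survival and RFS analysis on five years from randomization. Study Calendar footnote c follows survival to 3 years after end of treatment.

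**The concern.** EFS and RFS answer different questions. In AML, EFS is expected to register induction failure, and RFS describes how long a remission lasts. Section 13.3 collapses them into one quantity that does neither job: its event list leaves out induction failure, and its clock starts before there is any remission to lose. An analyst who follows 13.3 and one who follows 1.2.4 would report different EFS and RFS from the same data, and each could claim to be following the protocol. In an open-label trial, choosing between the two after seeing data would be hard to defend.

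The follow-up conflict differs in kind, because data that were never collected may not be recoverable when the analysis is due.

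**Working it through.** **1. The plan's own figure.** The only stated power is for the primary endpoint: 25 per arm, 50% vs 75%, one-sided alpha 0.1. With pooled variance under the null, z = [0.25 − 1.2816 × √(2 × 0.625 × 0.375 / 25)] / √[(0.25 + 0.1875) / 25] = (0.25 − 0.1755) / 0.1323 = 0.563, so power is 71.3%. This reproduces the stated figure of about 71%. None of EFS, RFS, DOR or OS enters the calculation, and no power or event target is given for them.

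**2. Definitions side by side.**

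| Endpoint | 1.2.4 and 1.2.5 | 13.3 | Difference |
|---|---|---|---|
| EFS | Randomization; no CR/CRi, relapse or death | Initial treatment; relapse or death | Induction failure is lost as an event |
| RFS | First CR/CRi; relapse or death | Initial treatment; relapse or death | Clock starts before remission |
| DOR | First CR/CRi | First CR | CRi not named; possibly shorthand |
| OS | Randomization | Initial treatment | About a week; minor |

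**3. Consequence for EFS.** Appendix D ties relapse to a prior remission: "Hematologic relapse (after CRMRD⁻, CR, CRi) Bone marrow blasts". Its molecular relapse likewise requires an earlier MRD-negative CR. Section 7.1.1 takes patients without CR/CRi off study. A patient who never remits therefore cannot relapse, and under 13.3 EFS runs on to death or censoring. Under 1.2.4 the same patient has an event.

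**4. How many patients.** Number not remitting = 50 × (1 − CR rate), using the background rates in 2.1.1.1 (60 to 70% under age 60; 35 to 50% in older or adverse-karyotype patients) and 2.3.1.2 (70 to 80% in younger adults).

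- CR 80%: 50 × 0.20 = 10
- CR 60%: 50 × 0.40 = 20
- CR 50%: 50 × 0.50 = 25
- CR 35%: 50 × 0.65 = 32.5

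The last two lines apply a subgroup rate to all 50 patients, so they show direction and are not a forecast. Eligibility runs to age 75 and admits therapy-related AML and AML after MDS, but the enrolled mix is not stated. The rates are for CR, and adding CRi would lower the counts. Early deaths are events under both definitions and come off the counts.

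**5. Consequence for RFS.** The end-of-induction marrow falls between Day 28 and Day 42 (calendar footnote n). Starting at initial treatment adds 28/7 = 4 to 42/7 = 6 weeks per remitter, and more where 7.1.1 has the marrow repeated every two weeks.

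**6. OS origin.** Section 7.1.1 allows randomization up to one week after 7+3 begins. Section 4.4 allows treatment up to 7 days after registration. If registration and randomization coincide (an assumption), the two origins differ by about a week in either direction.

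**7. Follow-up length.**

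- Section 7.4: 5 years.
- Section 10.1 collection: 3 years, which is 5 − 3 = 2 years short of the planned analysis.
- Footnote c, patient stopping after induction at day 42: 3 + 42/365.25 = 3.11 years.
- Footnote c, patient completing maintenance, short case (35 days induction, four 28-day cycles, 2 years): 3 + (35 + 112 + 730.5)/365.25 = 5.40 years.
- Footnote c, long case (42 days induction, 28-day gap, four 42-day cycles, 2 years): 3 + (42 + 28 + 168 + 730.5)/365.25 = 5.65 years.

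Five-year data are therefore not assured under 10.1 for anyone, nor under footnote c for patients who stop early.

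**The case against.** The best defence is that the objectives are clear and a competent analyst would follow them, treating 13.3 as loose summary text. The endpoints are secondary, with no stated power or between-arm test, and sites more plausibly work from 7.4 and the calendar than from the statistics section. That limits the harm. It does not remove the contradiction, since 13.3 is written as the calculation rule and nothing ranks the sections.

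Some stronger readings are tempting, and the documents do not support them:

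- *That 10.4.1.1 also redefines EFS.* Its clause can attach to RFS alone, as the parallel clause in 1.2.4 does. What is certain is that it starts RFS at initial treatment. Only 13.3 clearly merges the two endpoints.
- *That RFS under 13.3 includes patients who never remitted.* Section 13.3 names no RFS population. The text shows a wrong start date and no more.
- *That 20 of 50 is a ceiling on affected patients.* It rests on rates for younger adults, and the lower rates in 2.1.1.1 would exceed it.
- *That RFS and DOR have two contradictory censoring rules.* Section 10.1 censors DOR at the last evaluable disease assessment. The later sentence on last date known alive reads like ordinary OS wording. There is a conflict only if that sentence is meant to cover RFS, which is not stated.
- *That having both RFS and DOR is an error.* Under 1.2.4 and 1.2.5 they coincide among remitters. That is redundancy, and whether to report one or both is a choice.

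**Conclusion.** The point holds. Section 13.3 contradicts 1.2.4 on the EFS event and on the origins of EFS and RFS, and 10.4.1.1 repeats the initial-treatment start at least for RFS. Followed as written, 13.3 gives non-remitters no EFS event before death and lengthens each remitter's RFS by about 4 to 6 weeks or more. The count of 10 to 20 of 50 is illustrative: it assumes background CR rates of 60 to 80%, is reduced by early deaths, and would be larger in an older or adverse-karyotype population. The OS shift is minor, and the DOR wording may be shorthand.

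The follow-up conflict also holds: the collection limit in 10.1 falls two years short of the analysis planned in the same paragraph.

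A reader might infer that the trial's main result is in doubt. It is not. The primary endpoint is a response rate after the first consolidation cycle, and neither its definition nor its 71% power depends on these passages. This should be fixed before analysis, but it is not a design flaw.

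**What to change.** 1. Replace the wording in 13.3 and 10.4.1.1 with the definitions in 1.2.4 and 1.2.5. EFS runs from randomization to the first of not reaching CR/CRi, relapse, or death. RFS and DOR run from first CR/CRi among patients who reach it. OS runs from randomization.
2. Pre-specify one rule, identical in both arms, for when induction failure is declared and how it is dated. Section 1.2.4 gives no date, and the relevant passages do not point to one moment: 7.1.1 (marrow at count recovery, by day 42 without recovery, repeated every two weeks if hypoplastic), 10.5.2 (no CR/CRi after induction and first consolidation) and Appendix D (no CR/CRi after two induction courses). These must be reconciled for endpoint purposes. Dating failure at randomization is one option; the documents do not dictate it.
3. State that RFS and DOR coincide under these definitions and give them the same censoring rule. Section 10.1 names no censoring rule specifically for EFS, so add one at the same time.
4. Change the 10.1 collection limit to 5 years from randomization, and revise footnote c so that every patient is followed to at least 5 years from randomization.

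The cost is protocol wording: no added patients, visits or assays, and no follow-up beyond what 7.4 already commits to. One small downside should be acknowledged. If footnote c were strictly capped at 5 years, patients who complete maintenance would lose the 0.40 to 0.65 years (about 5 to 8 months) that it now gives them. Wording it as a minimum avoids that.
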